Programming Notes: Use the same layout as Table 14.3.4.1.3 – change ALT to AST and population to the safety population

Figure 14.3.4.2.5 – Boxplots of Laboratory Parameters by Study Day and Treatment: Aspartate Aminotransferase (AST) (U/L) – ITT Population

Programming Notes: Use the same layout as Table 14.3.4.1.5 – Change ALT to AST

Figure 14.3.4.2.6 - Boxplots of Laboratory Parameters by Study Day and Treatment: Aspartate Aminotransferase (AST) (U/L) – Safety Population

Programming Notes: Use the same layout as Table 14.3.4.1.5 – change ALT to AST and population to the safety population

Table 14.3.4.3.1 - Summary of Alkaline Phosphatase (U/L) by Study Day and Treatment – ITT Population

Programming Notes: Use the same layout as Table 14.3.4.1.1 – Change ALT to AST

Table 14.3.4.3.2 - Summary of Alkaline Phosphatase (U/L) by Study Day and Treatment – Safety Population

Programming Notes: Use the same layout as Table 14.3.4.1.1 – change ALT to AST and population to the safety population

Table 14.3.4.3.3 – Shift of Alkaline Phosphatase (U/L) by Study Day and Treatment – ITT Population

Programming Notes: Use the same layout as Table 14.3.4.1.3 – Change ALT to AST

Table 14.3.4.3.4 - Shift of Alkaline Phosphatase (U/L) by Study Day and Treatment – Safety Population

Programming Notes: Use the same layout as Table 14.3.4.1.3 – change ALT to AST and population to the safety population

Figure 14.3.4.3.5 – Boxplots of Laboratory Parameters by Study Day and Treatment: Alkaline Phosphatase (U/L) – ITT Population

Programming Notes: Use the same layout as Table 14.3.4.1.5 – Change ALT to AST

Figure 14.3.4.3.6 - Boxplots of Laboratory Parameters by Study Day and Treatment: Alkaline Phosphatase (U/L) – Safety Population

Programming Notes: Use the same layout as Table 14.3.4.1.5 – change ALT to AST and population to the safety population

Table 14.3.4.3.1 - Summary of Gamma-glutamyl Transpeptidase (GGT) (U/L) by Study Day and Treatment – ITT Population

Programming Notes: Use the same layout as Table 14.3.4.1.1 – Change ALT to AST

Table 14.3.4.3.2 - Summary of Gamma-glutamyl Transpeptidase (GGT) (U/L) by Study Day and Treatment – Safety Population

Programming Notes: Use the same layout as Table 14.3.4.1.1 – change ALT to AST and population to the safety population

Table 14.3.4.3.3 – Shift of Gamma-glutamyl Transpeptidase (GGT) (U/L) by Study Day and Treatment – ITT Population

Programming Notes: Use the same layout as Table 14.3.4.1.3 – Change ALT to AST

Figure 14.3.4.3.4 - Shift of Gamma-glutamyl Transpeptidase (GGT) (U/L) by Study Day and Treatment – Safety Population

Programming Notes: Use the same layout as Table 14.3.4.1.3 – change ALT to AST and population to the safety population

Figure 14.3.4.3.5 – Boxplots of Laboratory Parameters by Study Day and Treatment: Gamma-glutamyl Transpeptidase (GGT) (U/L) – ITT Population

Programming Notes: Use the same layout as Table 14.3.4.1.5 – Change ALT to AST

Figure 14.3.4.3.6 - Boxplots of Laboratory Parameters by Study Day and Treatment: Gamma-glutamyl Transpeptidase (GGT) (U/L) – Safety Population

Programming Notes: Use the same layout as Table 14.3.4.1.5 – change ALT to AST and population to the safety population

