4.1.6 Handling of Baseline Differences

Group differences in baseline characteristics will be evaluated. Analyses will be performed to evaluate the treatment effect controlling for baseline covariates found to have clinically meaningful baseline differences. Clinically meaningful will be determined by the Sponsor Study Safety Monitor or Primary Investigator. This will be done using a generalized linear model with parameters estimated using SAS PROC GENMOD with distribution set to *binomial* and link set to *logit*. The adjusted probabilities and their standard errors are determined on the probability scale using the *ilink* option in a *lsmeans* statement with a *diff* option. This statement produces a test for the treatment group difference controlling for other covariates in the model. The model will include treatment group and each identified covariate one-at-a-time. The standard error on the probability scale for the difference in event rates will be determined as the square root of the sum of the treatment group specific squared standard errors and used in the determination of the 95% CI.

As requested by FDA, multivariable analyses will be provided to the degree that sample size and number of observed events in each group allow. It is understood that a total of 10 events per covariate is necessary for this modeling approach, which limits the number of covariates the model can support. The full model will consist of age, BMI, sex, and the number of days since first COVID-19 symptom (≤ 5 or > 5 days), in addition to treatment group (sample size permitting). In addition to the full model, a forward stepwise procedure will be used to identify a set of covariates that each provide some independent association with the primary outcome.

The totality of evidence (i.e., the clinical and statistical interpretations) will provide support for decision making regarding Phase III investigation.

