[figure not shown]
	Number and Percentage with Endpoint						p-value ²	Difference and Confidence Interval (%) ³		
	Camostat mesilate			Placebo				Diff.	LB	UB
Hospitalization/ER visit or death within 28 Days	N	n	%	N	n	%				
Adjusted for baseline covariates with clinically significant group differences ⁴										
Adjusted for all covariates ⁵										
Model identified by stepwise ⁶										

Notes:
 
¹ The Intent-to-Treat (ITT) population will include all subjects who are randomized. Subjects will be analyzed according to their study treatment assignment, not according to the treatment actually received (N=295).
 
² Unadjusted chi-square test
 
³ Two-sided 95% CI
 
⁴ Variable list
 
⁵ Variable list
 
⁶ Variable list
 
Program Source [xxxxxxx.sas]
										

**DRAFT Table 14.2.3
Time to Resolution of Fever
Intent-To-Treat Population**

Interval	Pts at start	#with event	Censored	Cumulative Resolution Rate	SE[‡]
At Start					
Day 1					
...					
Day 14					
Notes: [‡] SE Errors computed using the Peto method. No subjects died on or before Day14. Program source:					

Programming Notes: Time to Resolution of New Fever will be displayed in a similar manner.

**DRAFT Figure 14.2.4
Kaplan-Meier Time to Resolution of Fever
Intent-to-Treat Population**

Program Name: XXXXXX.sas

Database lock date: 17JAN2020; Run Date: 30MAR2021

Note: This figure will include a number At-Risk Table detailing the number of subjects with events and censored for each day of the analysis. Day 0 will be included displaying the number of subjects in the analysis overall.

Programming Notes: Kaplan-Meier Time to COVID-19 Hospitalization/ER visit will be displayed in similar manner.

DRAFT Table 14.2.5
Time to COVID-19 Hospitalization/ER visit or Death
Intent-To-Treat Population

Interval	Pts at start	#with event	Censored	Cumulative Rate	SE[‡]
At Start					
Day 1					
...					
Day 28					

Notes: [‡] SE Errors computed using the Peto method. Program source:
					

**DRAFT Table 14.2.8.1
Shift Table of Fever Severity Categories by Study Day and Treatment**

		Camostat mesilate											Placebo												
		(N=xxx)											(N=xxx)												
		None		Grade 1		Grade 2		Grade 3		Grade 4		Missing		None		Grade 1		Grade 2		Grade 3		Grade 4		Missing	
Study Day		n	%	n	%	n	%	n	%	n	%	n	%	n	%	n	%	n	%			n			%
Day 0	--	xx	xx.x	xx	xx.x	xx	xx.x	xx	xx.x	xx	xx.x	xx	xx.x	xx	xx.x	xx	xx.x	xx	xx.x	xx	xx.x	xx	xx	xx.x	xx.x

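### SAP 4.1.6 fits imbalanced baseline covariates one at a time, but row 1 of draft Table 14.2.1.4 shows one result for a list of them; with two or more flagged, joint control is not guaranteed

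*SAP*

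**What the plan says.** SAP 4.1.6 (Handling of Baseline Differences) sets the aim in the plural: to evaluate the treatment effect "controlling for baseline covariates found to have clinically meaningful baseline differences". The choice of covariates is a judgement with no numerical threshold: "Clinically meaningful will be determined by the Sponsor Study Safety Monitor or Primary Investigator". The method is a logistic model, and on how the covariates enter it the SAP is explicit: "The model will include treatment group and each identified covariate one-at-a-time".

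The same section then adds two multivariable analyses, as far as sample size and events allow. One is fixed: "The full model will consist of age, BMI, sex, and the number of days since first COVID-19 symptom", plus treatment. The other is data-driven: "a forward stepwise procedure will be used to identify a set of covariates that each provide some independent association with the primary outcome". A limit is given: "It is understood that a total of 10 events per covariate is necessary for this modeling approach".

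Draft Table 14.2.1.4 in the SAP appendix has three rows. Row 1 is "Adjusted for baseline covariates with clinically significant group differences", row 2 is the all-covariate model and row 3 is the stepwise model. Each row has one p-value, one difference and one confidence interval. Row 1 is footnoted "⁴ Variable list", in the same form as the two multivariable rows. The appendix's list of tables repeats the analysis for PP1 and PP2 as Tables 14.2.1.5 and 14.2.1.6.

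**The concern.** A model with one covariate removes that covariate's imbalance and leaves the others in the treatment estimate. If two or more prognostic factors are flagged, the stated method does not do what the section sets out to do. It also produces several estimates where the table has room for one, and nothing says whether they are all shown, combined, or replaced by the joint model that the footnote suggests.

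At stake is the reading of a robustness check. Row 1 is where a reader will look to see whether the effect survives control for chance imbalance, and 4.1.6 closes by saying that the evidence as a whole will inform the Phase III decision.

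**Working it through.** **1. Text against table.** With k flagged covariates, 4.1.6 gives k models, hence k differences, k intervals and k p-values. Row 1 takes one of each. For k = 1 the two agree. For k of 2 or more they do not, and no rule links them.

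**2. What the other rows cover.** Row 2 adjusts jointly for age, BMI, sex and symptom days, so imbalances confined to those four are handled together, provided the events allow that model. Row 3 selects on association with outcome, so an imbalanced factor may or may not enter. Draft Table 14.1.2.1.1 also summarises race, ethnicity, diabetes, hypertension, lung, cardiac and liver disease, and number of risk factors. Several of these are enrolment risk factors in Protocol 8.1. An imbalance in two of them is not assured joint control in any row.

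**3. Event budget.** SAP 4.1.3 expects nearly 28 events per arm. This reproduces: 186 × 0.15 = 27.9 and 93 × 0.30 = 27.9, total 55.8. At 200:100 the total is 30 + 30 = 60. At 10 events per term, 55.8/10 = 5.6 and 60/10 = 6.0. That is five to six terms, or treatment plus about four covariates.

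**4. Size, by illustration.** The event rates and allocation are the SAP's. All other inputs are assumed: independent binary risk factors, pooled prevalence 40%, odds ratio 2.5 each, and each factor 10 points more common on camostat (43.3% against 33.3%, since 2/3 × 43.3 + 1/3 × 33.3 = 40). The SE of such an imbalance is √(0.4 × 0.6 × (1/200 + 1/100)) = 0.060, so 10 points is about 1.7 SE. The model is logit(p) = a + t·treatment + ln(2.5)·(number of factors present), with a and t solved to give 30% and 15% over the pooled covariate distribution. Each model is fitted to the expected data, and the risk difference is averaged over that distribution.

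| Factors imbalanced | Unadjusted | Each one-covariate model | Joint model |
|---|---|---|---|
| Two | −11.8 | −13.4 | −15.0 |
| Three | −10.4 | −11.9 | −15.0 |

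With two factors the one-covariate fit leaves 15.0 − 13.4 = 1.6 of the 3.2 points of bias, one half. With three it leaves 3.1 of about 4.6 points, two thirds. Over odds ratios of 2 to 3 and imbalances of 8 to 12 points, the residual runs from 1.0 point (two factors, the low ends) to 4.3 points (three factors, the high ends).

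The direction depends on which arm carries the excess. With no true effect, a 30% placebo rate, two factors at 40% on camostat against 50 to 55% on placebo, and odds ratios of 1.5 to 3, the unadjusted bias is −1.7 to −6.0 points in favour of camostat. One-covariate models leave −0.8 to −3.0 points and the joint model leaves 0.0.

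**5. Yardstick.** The SE of the difference at 200:100 is √(0.15 × 0.85/200 + 0.30 × 0.70/100) = √0.0027375 = 0.052, or 5.2 points. The residuals are therefore about 0.2 SE (1.0/5.2) to 0.8 SE (4.3/5.2).

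**6. How the risk difference is averaged.** SAP 4.1.6 back-transforms least-squares means. In the two-factor case, the joint model evaluated at the observed covariate means gives −15.1. If binary covariates are coded as class variables and averaged with equal weights (an assumption about coding), the joint model gives −16.8 and the one-covariate model −14.1, against a true −15.0. Joint fitting alone does not guarantee the right figure.

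**The case against.** The analysis is supportive. SAP 4.1.1 makes an unadjusted test primary, and no success criterion rests on row 1. The problem needs at least two flagged covariates, and imbalance in a randomised trial is chance. Treating the seven risk factors of Protocol 8.1 as independent (an assumption), the chance of at least two being 1.7 SE or more out of balance in the same direction is about 8%, and of at least three about 0.7%. The residual bias is under one SE. One covariate at a time is also a reasonable economy when events are few: with about 20 events, the SAP's own rule allows treatment plus one covariate and no more. All of this stands, and it sets the priority.

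Three stronger readings are tempting, and the documents do not support them:

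- A reader might infer that nothing in the table removes a combined imbalance. Row 2 does so when the imbalances lie within its four covariates.
- A reader might infer that someone must pick one of several results once the arms are known. The appendix marks its shells as drafts with layouts open to revision, so one labelled line per covariate could be printed. The choice is unspecified, not forced.
- A reader might infer that the primary result is compromised. It does not use these models.

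The objection does not remove the mismatch itself. The section states an aim, then a rule that misses the aim when two or more covariates are flagged, and the table implies a different rule.

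**Conclusion.** The point holds within limits. When two or more prognostic covariates are flagged and at least one is outside age, BMI, sex and symptom days, no specified model is guaranteed to control for them together, and the content of row 1 is undefined. The cost is 1.0 to 4.3 points of residual bias in a supportive estimate, against an SE of about 5.2 points. That range rests on assumed odds ratios, prevalence, independence and same-direction imbalances, none of which the documents give. A joint model fits the planned event budget only if the 15% and 30% planning rates are roughly right. This is a cheap improvement of low priority.

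**What to change.** In SAP 4.1.6, replace the one-at-a-time sentence with these rules:

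- All covariates flagged as imbalanced enter one logistic model with treatment, up to the limit of 10 events per covariate (about five terms at 56 to 60 events).
- If more are flagged than the limit allows, the list is cut in an order fixed before unblinding.
- If events allow only one covariate, one labelled line per covariate is shown.
- The risk difference is averaged over the observed covariate distribution, not over equal-weight margins.

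Report the joint model in row 1 of Tables 14.2.1.4 to 14.2.1.6 and keep the one-covariate fits as extra output. In the same edit, correct the p-value footnote of Table 14.2.1.4, which labels the adjusted rows as an unadjusted chi-square test although 4.1.6 describes a model-based one.

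The cost is a few sentences of SAP text, one model call per population, and an interval calculation that matches the averaged difference. The downsides are that the cut order has to be agreed in advance and that the joint model is less stable if events are few.
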